### Background & Purpose of Research

## Describe the purpose, specific aims or objectives and specify the hypotheses or research questions to be studied:

For this study, we hypothesize that use of movable wheelchair arm rest device during inpatient therapy will lead to significantly greater improvements in UE motor recovery than conventional treatment. (For a demonstration video of the movable wheelchair arm rest device, please visit: <https://youtu.be/RfbaOGhJfug>). Our Aim is to perform a randomized controlled trial of the movable wheelchair arm rest device with inpatients with subacute stroke in three different inpatient rehabilitation facilities (N=58; Months 6-24). UCI will be one of the study sites. Rancho Los Amigos Rehabilitation center and Casa Colina Hospital and Centers for Healthcare will potentially be the other two study sites. We are in the process of negotiating the contracts between sites. Participants will be >3 days and <3 weeks post-stroke, with initial FM scores <4239. Participants will be randomized to receive the movable wheelchair arm rest device or an electronic exercise program and instructed to practice moving their arm between therapy sessions. The primary outcome measure will be change in FM score from baseline to three-months post-stroke. We hypothesize that participants who receive movable wheelchair arm rest device will have significantly greater improvements in FM score than control ( $p < 0.05$ , RM-ANCOVA) without an increase in pain or spasticity, if they exceed the putative threshold of UE motor drive needed for recovery. Success Criteria: A significantly greater increase in FM of >4.25 points (the FM MCID40) between movable wheelchair arm rest device and control at three months.

At project end, we will have validated the clinical feasibility and efficacy of the movable wheelchair arm rest device and optimized it for production and mass distribution. If our plan is successful, we will have demonstrated that wheelchair-based "rocking therapy" can help patients routinely achieve the threshold level of sensory motor drive needed to provoke true UE recovery.

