## Sample Size Determination:

1. Explain how the overall target sample size was determined (e.g., power analysis; precision estimation). Power analysis should (at least) match the primary outcome/endpoint.
2. Provide justification of the effect size for the primary outcome based on preliminary data, current knowledge/literature and/or cost consideration.
3. If appropriate, provide sample size justification for secondary outcomes.

Based on a power analysis using data from our previous LARA RCT with individuals with subacute stroke (n=19)36, enrolling 29 participants in each group, brings a total of 58 from 2 groups, will provide an 80% chance to demonstrate a significant difference in FM between the device and control at the three-month follow up ( $\alpha = 0.05$ ), assuming a dropout rate of 10%.

---

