## **Describe the statistical methods for the stated specific aims and hypotheses. The analysis plans should match the stated study specific aims and hypotheses:**

All reported data from this study will be disaggregated by sex to test for any potential bias due to this biological variable. Data will be analyzed using modified intention-to-treat analysis. That is, all participants will be included in the analysis if the follow-up assessment is available, regardless of any deviations from the protocol. The effect of treatment on the primary outcome measure will be assessed using a repeated measures analysis of covariance (RM-ANCOVA) to account for any baseline differences between groups or variability in treatment intensity, with follow-up comparisons performed using Bonferroni-corrected t-tests or Wilcoxon rank sum tests if the data violates the assumption of normality. We hypothesize the participants in the movable wheelchair arm rest device group will have significantly greater and clinically meaningful (i.e. >4.25 FM points) reductions in motor impairment than participants in the control group due to the increased dose of UE motor system activation. Using data from the sensors on movable wheelchair arm rest device, we will test if this effect depends nonlinearly on the number of repetitions performed with the device, consistent with recent meta-analyses of forelimb recovery in a rodent model of stroke. That is, we hypothesize that the movable wheelchair arm rest device will provide a benefit only if the dose exceeds a threshold. A key goal is to also identify that threshold (by making a graph for humans like the one for rats), which will enable us to move forward with effective clinical prescription and goal setting with the movable wheelchair arm rest device. Visual analog pain, spasticity, and FAC scores will also be analyzed using RM-ANCOVA to test for significant changes related to use of the device. All analyses will be reviewed by a statistical consultant in the Institute for Clinical and Translational Science at UC Irvine.

**Provide precise definitions of the study endpoints and criteria for evaluation; if the primary outcomes are derived from several measurements (i.e., composite variables) or if endpoints are based composite variables, then describe precisely how the composite variables are derived:**

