**Describe the statistical method(s) that will be used to analyze the primary outcome(s) or endpoints:**

t-tests with Bonferroni corrections, or Wilcoxon rank sum tests if the distributions fail the Lilliefors test for normality.

**If appropriate describe secondary or post hoc analyses of primary outcome(s) or other exploratory analysis and if necessary, provide a breakdown of the methods used per outcome or endpoint:**

The effect of treatment on each outcome measure will be assessed using a repeated-measures ANOVA

---

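### The 80% power is stated at alpha 0.05, but the t-tests listed for the primary outcome are Bonferroni-corrected for an unstated number of comparisons; with two to four, power would be about 71% to 61%

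*Combined protocol and SAP*

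**What the plan says.** *Sample Size Determination* bases the size on a previous pilot trial ("Based on a power analysis using data from our previous LARA RCT with individuals with subacute stroke"). It states that "enrolling 29 participants in each group, brings a total of 58 from 2 groups" and that this "will provide an 80% chance to demonstrate a significant difference in FM between the device and control at the three-month follow up". Alpha is 0.05, dropout is 10%, and no multiplicity adjustment is mentioned. The effect size, standard deviation, sidedness and test are not given.

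Three other places in the same document describe how the primary FM outcome is tested:

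- *Background & Purpose of Research* defines the outcome as change in FM from baseline to three months and attaches p < 0.05 to an RM-ANCOVA. It then sets the bar: "Success Criteria: A significantly greater increase in FM of >4.25 points" between device and control at three months.
- *Study Design & Statistics*, statistical methods for the aims, also assesses the primary outcome by RM-ANCOVA, "with follow-up comparisons performed using Bonferroni-corrected t-tests or Wilcoxon rank sum tests if the data violates the assumption of normality".
- *Study Design & Statistics*, method for the primary outcome, lists only "t-tests with Bonferroni corrections, or Wilcoxon rank sum tests if the distributions fail the Lilliefors test for normality". Repeated-measures ANOVA appears in the next field, for secondary, post hoc or exploratory analyses.

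None of these says how many comparisons the Bonferroni correction covers. The design schedules three evaluations: baseline, discharge and three months post-stroke.

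**The concern.** The power statement concerns one contrast at one time point, at 0.05. The method listed for that outcome is a corrected test. With two or more comparisons, a Bonferroni-corrected test is not run at 0.05, so the stated power is not the power of the listed test.

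The decision rule is also at stake. Let k be the number of comparisons. Suppose the three-month comparison shows a difference above 4.25 points with a p-value between 0.05/k and 0.05. That meets the criterion in the aims but fails under the primary-outcome field. With p = 0.03, for example, any k of two or more reverses the conclusion. Because k is not stated, a reader cannot tell in advance which result counts.

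**Working it through.** **Inputs.** From *Sample Size Determination*: 29 per arm, 10% dropout, alpha 0.05, power 80%. Assumed here: a two-sided two-sample t-test, and k = 2, 3 or 4. The three scheduled evaluations suggest two (the post-baseline visits) or three; four is shown for range. No value of k is in the documents.

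**The plan's own figure.** The dropout step is coherent: 29 × 0.9 = 26.1, so 26 evaluable per arm, and 26 / 0.9 = 28.9, which rounds up to 29. The 80% itself cannot be reproduced, because effect size, standard deviation, sidedness and test are not given. It is taken as correct for one uncorrected test.

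**Step 1: the standardised difference that 80% implies.** With n = 26 per arm, the noncentrality is d × √(n/2) = d × √13 and there are 2n − 2 = 50 degrees of freedom. Power is the probability that a noncentral t variable falls beyond ± the critical value. Setting this to 0.80 at two-sided 0.05 gives d = 0.792. The normal approximation gives (1.960 + 0.842) / √13 = 0.777.

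**Step 2: keep that difference and change only alpha, to 0.05/k.** In the normal approximation, power = Φ(2.802 − z), where z is the upper 0.05/(2k) point.

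| k | Alpha per comparison | z | Power, normal | Power, noncentral t |
|---|---|---|---|---|
| 1 | 0.05 | 1.960 | 80.0% | 80.0% |
| 2 | 0.025 | 2.241 | 71.2% | 70.7% |
| 3 | 0.0167 | 2.394 | 65.8% | 64.8% |
| 4 | 0.0125 | 2.498 | 61.9% | 60.6% |

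**Sensitivity.** With 29 per arm and the difference re-solved to give 80%, noncentral-t power is 70.7% for k = 2 and 64.9% for k = 3, so the loss hardly depends on n. One-sided, it is 69.6% and 63.1%.

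**Size needed to restore 80% at the same difference (two-sided).** For k = 2, 32 evaluable per arm (32 / 0.9 = 35.6, so 36 enrolled). For k = 3, 35 evaluable (35 / 0.9 = 38.9, so 39 enrolled).

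**The case against.** A reader might infer three stronger things, and the documents support none of them.

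*That the trial simply has 65% to 71% power.* This needs k to be two or three, and k is not stated. With one primary outcome, one contrast and one decision time, k could be one. Bonferroni then changes nothing and power stays at 80%. Three comparisons is also debatable if it counts a baseline difference, which is not a treatment comparison. The 0.05 in the power statement could be a familywise level already allowed for, and the missing inputs prevent a check. The range must therefore be stated as conditional.

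*That the corrected t-test is the only stated test of the three-month difference.* RM-ANCOVA is named twice for the primary outcome, once with p < 0.05. Its time points are not given. If only baseline and three months enter, its group-by-time test isolates the contrast without correction. If discharge also enters, the overall test does not isolate it, and the comparison that would do so is a corrected one. Even on the favourable reading, the primary-outcome field still names a different test. It is also unclear whether the correction applies to the Wilcoxon alternative.

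*That a p-value between 0.05/k and 0.05 is by itself a success under the aims.* The criterion also requires a difference above 4.25 points.

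A further objection is practical. The renewal form reports 37 adults (2 + 12 + 23 across the three sites), not 58. At d = 0.792, even an uncorrected two-sided test with 37 analysed would have about 65% power, so planned power no longer describes this trial. That stands, and it moves the weight of the point to the decision threshold, which is still live. Removing a correction after data collection also relaxes the rule in one field of the plan, so it has to be done openly.

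**Conclusion.** The conflict is real. The power statement uses 0.05 for the three-month FM contrast, the primary-outcome field uses a Bonferroni correction of unstated size, and the aims and general methods name RM-ANCOVA. If the 80% is a two-sided uncorrected t-test with 26 evaluable per arm, it becomes about 71%, 65% or 61% with two, three or four comparisons, and is unchanged only with one. These figures rest on the assumed test, sidedness and k. That the passages disagree on the primary test and leave its threshold undefined rests on none of them. This is a mismatch of specification, not an arithmetic slip in the sample size.

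**What to change.** Reconcile the aims, the statistical methods and the primary-outcome field by naming one primary test of the device-control FM contrast at three months. A baseline-adjusted analysis would suit, since the plan already intends to account for baseline differences. Test that contrast once, at two-sided 0.05. Confine Bonferroni to the discharge-visit and other follow-up comparisons, and state that these cannot trigger success.

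If the correction is kept on the primary contrast, state the number of comparisons and restate the power in *Sample Size Determination* to match.

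*Enrollment Status* and *Progress Report* say that enrolment, procedures and follow-up are complete and analysis is under way. Date the change, and state whether FM results by arm had been seen when it was made.

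The cost is a few sentences in the plan, or a lower stated power if the correction stays. No further participants or visits are needed.

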## Eligibility Criteria

**IMPORTANT!** If utilizing [UCI Health Enterprise Data & Analytics](#) services, include specific timeframes for each eligibility factor, as applicable.

### Example:

1. Birth sex: female
2. Age:  $\geq 18$  years old as of 2020-01-01
3. The result of the most recent SARS-CoV-2 test (of any type), performed between 2020-01-01 and 2020-12-31, was positive
4. With any sub-classification of type 2 diabetes (E11\*) diagnosed at any date prior to 2020-01-01
5. Did NOT have an ED visit between 2020-01-01 and 2020-12-31

**Inclusion/Exclusion Criteria: Identify the factors for limited eligibility and provide a scientific rationale.**

---

## Category/Group Eligibility

Adults with stroke

### Inclusion Criteria

- 18 to 84 years of age
- Experienced a single stroke or multiple strokes >3 days and < 3 weeks prior to study enrollment. For participants with bilateral involvement, PI will define an index side (i.e.: the side that is affected by the most current stroke). If the participant's current stroke is bilateral in nature, then PI would identify the index side as the one with the lower FM score. Ultimately, the training therapists will determine which UE should be trained with Boost and that UE should remain the same throughout the study.
- Currently admitted or accepted into Acute Rehabilitation program for stroke
- UE FM <42/66
- Absence of moderate to severe shoulder pain while using the movable wheelchair arm rest device (<6 on the 10-point visual analog pain scale)
- Absence of severe tone at the affected UE (score <4 on the Modified Ashworth Spasticity Scale)
- Deem to be an appropriate candidate for manual wheelchair by ARU clinicians.

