## **Describe the primary outcome variable(s), secondary outcome variables, and predictors and/or comparison groups as appropriate for the stated study objectives/specific aims:**

### **Primary outcome measure**

The primary outcome measure will be the change in Fugl-Meyer Arm Motor Assessment Score (FMAMA) from baseline to three-month post-stroke to assess increases in motor recovery of the upper extremity.

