## Provide a detailed chronological description of the procedures:

Participants will be invited for an initial assessment within three days of admission to an IRF to confirm they meet the inclusion criteria and to establish a baseline measure. Those who qualify will be randomly assigned to either the movable wheelchair arm rest device group or the control group. To ensure matched levels of impairment between groups, subjects will be stratified by their FM score into two levels (0-21, 22-42) and then randomized by alternating block allocation based on the time of enrollment. Individuals in the device group will be provided with a wheelchair equipped with movable wheelchair arm rest device and trained how to use it to perform stationary reaching practice and to help them ambulate. Once participants are competent, they will be instructed to perform stationary reaching practice and to use the movable wheelchair arm rest device to ambulate around the inpatient facility, with a target dose of 1000 device "reps" per day, which we estimate will take about 30 minutes of device use at around 1 rep every 2 seconds. The supervising therapist will customize the range of motion needed for device's integrated electronics to count a "rep" based on each patient's abilities. Participants in the control group will be given an electronic home exercise program (HEP) of proximal arm exercises developed by study therapists. They will be encouraged to exercise for 30 minutes a day with the electronic HEP (i.e. to match the duration with device). A supervising therapist will check in with all participants once per week to check on engagement with their exercise program and to troubleshoot any issues with device or the electronic exercise program. To measure compliance and quantify dose, the device will report the date, time, and number of repetitions completed for each movement type (stationary/overground) throughout the study using integrated electronics. Using technology, we previously developed for another study, the electronic exercise program provided to control participants will record how long the book is opened each day with a hidden magnetic sensor and data logger. Participants in both groups will continue therapy for the duration of their inpatient stays (average length of stay for individuals with moderate to severe impairment is 14 to 22 days, respectively, based on 104, n = 4142). The actual length of stay for each participant will be quantified and included as a covariate in the data analysis. Once participants are discharged, they will receive a post-therapy assessment and they may be allowed to keep the device and the exercise program based on the therapists' recommendations for the duration of the study. Participants will return three months following stroke onset for a final assessment. We would like to utilize the Tenovi Gateway device to collect the amount of use data. This data will be automatically uploaded to secure web portal through a Tenovi Gateway device, which plugs into the wall at subjects' rooms at the Acute Rehab Unit and or subjects' homes, automatically communicates with the exercise repetition counts through bluetooth, then uploads the data to the web portal through a low-speed cellular data connection. A study team member may visit participants' homes to set up the devices.

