#### Data Points

**Specify the date-range of the data used for the project (e.g. January 2002 to January 2020):**

March 2023 to August 2024

Provide a **complete list** of ALL data points, variables, and/or information that will be collected (i.e. data abstraction form):

We will collect the date of stroke, type of stroke, sex, age of the participants and medical record numbers.

If the list of variables will be attached as a separate document [i.e. case report form (CRF; eCRF)], enter "See Attached" above and check the confirmation box below.

The list of variables is attached

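### Baseline is taken anywhere from about day 4 to day 20 after stroke and the endpoint is fixed at three months after onset, but no version of the primary analysis adjusts for days since stroke: a loss of precision, not a bias

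*Combined protocol and SAP*

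**What the plan says.** **Entry and baseline.** The Inclusion Criteria admit patients whose stroke occurred ">3 days and < 3 weeks prior to study enrollment". Project Procedures describes an "initial assessment within three days of admission to an IRF to confirm they meet the inclusion criteria and to establish a baseline measure", so baseline FM is measured at about the time of enrolment.

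**Endpoint.** The Primary outcome measure section defines the "change in Fugl-Meyer Arm Motor Assessment Score (FMAMA) from baseline to three-month post-stroke". Project Procedures adds: "Participants will return three months following stroke onset for a final assessment". The endpoint definition under Study Design & Statistics instead names the FM score at the three-month visit, with no subtraction of baseline. All of these time the visit from stroke onset, not from baseline.

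**Analysis.**
- The statistical methods section proposes a repeated-measures ANCOVA "to account for any baseline differences between groups or variability in treatment intensity", without listing covariates.
- The answer on analysing the primary outcome gives Bonferroni-corrected t-tests, or Wilcoxon rank sum tests if normality fails. These have no covariates.
- Project Procedures names one covariate outright: "The actual length of stay for each participant will be quantified and included as a covariate in the data analysis".
- The only stratifier is baseline FM in two levels (0-21 and 22-42).

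**Data.** The Data Points section says "We will collect the date of stroke, type of stroke, sex, age of the participants and medical record numbers".

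**The concern.** A patient assessed on day 4 has more of the early recovery period still ahead, and more time with the device or exercise programme before the final visit, than a patient assessed on day 20. The same baseline FM on those two days need not carry the same prognosis. The protocol's own background section rests on heightened plasticity early after stroke, so on its own argument time since stroke should predict the outcome.

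The plan reaches for treatment intensity and length of stay as adjusters. Both are measured after randomisation and could be affected by the arm. Days since stroke is fixed before randomisation, so adjusting for it is safe, and it is left out. At stake is efficiency in a small trial: variation in entry time that could be explained stays in the error term.

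**Working it through.** **1. Spread in the interval.** More than 3 days and less than 21 days is day 4 to day 20 in whole days. Taking three months as day 90 (an assumption), the interval is 90 − 4 = 86 days at one end and 90 − 20 = 70 at the other. The spread is 16 days, and 86/70 = 1.23.

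**2. The plan's sample size.** Sample Size Determination gives 29 per arm, 58 in total, 80% power, α = 0.05 and 10% dropout. It gives neither an SD nor a planning difference, so 58 cannot be reproduced. The dropout step is consistent: 26/0.90 = 28.9, rounded up to 29. For 26 evaluable per arm, two-sided (sidedness is not stated), the implied standardised effect is

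(1.960 + 0.842) × √(2/26) = 0.777.

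If the planning difference were the 4.25-point success criterion (an assumption), the implied SD is 4.25/0.777 = 5.47.

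**3. Effect of adding the covariate.** Let R² be the share of the remaining outcome variance explained by days since stroke. The residual SD is multiplied by √(1 − R²), and power = Φ(2.802/√(1 − R²) − 1.960). The documents give no R², so a range is shown.

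| Assumed partial R² | √(1 − R²) | Fall in standard error | Power, 26 per arm |
|---|---|---|---|
| 0 | 1.000 | – | 80.0% |
| 0.01 | 0.995 | 0.5% | 80.4% |
| 0.05 | 0.975 | 2.5% | 82.0% |
| 0.10 | 0.949 | 5.1% | 84.0% |
| 0.20 | 0.894 | 10.6% | 87.9% |

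A t-based calculation with one degree of freedom given up agrees to within 0.2 percentage points.

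**4. What those R² values mean.** If entry is uniform over the 17 whole days 4 to 20 (an assumption), the variance is (17² − 1)/12 = 24 and the SD 4.9 days. For a slope of b FM points per day, R² = 24b²/SD².

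| Assumed b | R² at SD 5.47 | R² at SD 10 |
|---|---|---|
| 0.1 | 0.008 | 0.002 |
| 0.25 | 0.050 | 0.015 |
| 0.5 | 0.20 | 0.06 |

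Here b is the slope left after baseline FM is in the model, which may be smaller than the raw recovery rate.

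**5. At achieved enrolment.** The renewal form reports 37 adults (2 + 12 + 23 over the three sites). If 10% are lost, that is 37 × 0.9/2 = 16.65 per arm, and power at the same implied effect is Φ(0.777 × √(16.65/2) − 1.960) = 61%. An R² of 0.05 to 0.20 raises it to 63% to 71%.

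**The case against.** The strongest reply is that leaving out a prognostic covariate does not invalidate a randomised comparison. That stands. Randomisation balances entry time on average, and both arms draw on the same window.

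A reader might nonetheless infer that chance imbalance in entry time could shift the FM difference by a sizeable part of 4.25 points. With the assumptions above, the SD of the difference in arm means at 26 per arm is 4.9 × √(2/26) = 1.36 days, so the 95% extreme is 1.96 × 1.36 = 2.7 days. At 0.5 points per day that is 1.3 points; at 0.1 it is 0.3. These are extremes, they rest on assumed slopes, and they apply to a change score not adjusted for baseline FM. The unadjusted standard error already contains this variation, so presenting it as an extra error counts it twice. The documents do not support that reading.

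Two further replies have some force. On the definition of the outcome as FM at three months, everyone is measured at the same time since stroke, and timing enters mainly through baseline FM. Once baseline FM is a covariate, analysing change or final score gives the same arm effect, so what matters is only what days since stroke adds beyond baseline FM. That is unknown and could be close to nothing. Second, the ANCOVA's stated aim of handling baseline differences could be read to include timing. But it names no covariate, and the t-test plan has none. Nor does blocking by time of enrolment help: it reads most naturally as calendar order, not time since stroke.

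**Conclusion.** The point holds as a missed and nearly free gain in precision. The facts are firm: a 16-day spread in the baseline-to-endpoint interval, a visit timed from stroke onset, a collected stroke date, and no mention of days since stroke in any version of the primary analysis. The size is not firm. Over an assumed partial R² of 0.01 to 0.20, power at the planned size gains from 0.4 to about 8 percentage points. The low end is more plausible if the outcome SD is well above 5.47 or if baseline FM already reflects timing. The calculation assumes a two-sided test, 26 evaluable per arm and 80% power without the covariate. Nothing here shows bias or makes the planned comparison invalid.

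**What to change.** Reconcile the repeated-measures ANCOVA and the t-test or Wilcoxon plan into one primary analysis: an ANCOVA of three-month FM on arm, continuous baseline FM and days from stroke onset to the baseline assessment. The FM stratum may be kept because it was used in the randomisation, though it is largely redundant with continuous FM. Use this pre-randomisation covariate in the primary model rather than length of stay or treatment intensity, which arise after randomisation.

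The cost is one degree of freedom for days since stroke, and no new data: the stroke date is collected, and the baseline assessment is a study visit whose date should be on file.

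Timing matters. The renewal form states that enrolment and procedures are complete and that analysis is in progress. Fix the model in a dated plan before anyone sees results by arm. If they have been seen, report the adjusted analysis as a labelled sensitivity analysis.
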